#### 4.2.6. *Norfolk Diabetic Quality of Life-Diabetic Neuropathy (QOL-DN)*

The Norfolk Diabetic QOL-DN is a 47-item, self-administered questionnaire designed to measure the relationship between symptomatic diabetic neuropathy and quality of life from the perspective of the patient. The questionnaire is composed of two parts: questions related to symptoms experienced by the patient and questions related to the impact of the patient's neuropathy on activities of daily life.

#### 4.2.7. *Use of rescue medication*

Use of rescue medication will be recorded by the patient in the daily diary beginning at the start of the pain observation period on Day -14 and ending on Week 12, the last day of the treatment period, or upon premature discontinuation as applicable.

#### 4.2.8. *Intraepidermal Nerve Fiber Density Determination (IENFD)*

There is a strong correlation between neuropathy severity and a reduction in intraepidermal nerve fiber density. Intraepidermal nerve fiber biopsy is an effective tool for defining pathological changes to nerve fiber density and may have the potential to assess drug effects in a smaller number of patients as compared with subjective, symptom-based pain assessments. Examination of IENFD is intended to help understand whether any observed

effects on pain and other neuropathic signs and symptoms are mediated by improvement in nerve function. It may also help assess whether ricolinostat has structural effects on peripheral nerves.

#### **4.3. Efficacy endpoints**

##### *4.3.1. Primary endpoint*

The primary efficacy endpoint for this study is change from baseline in mean average pain intensity following 12 weeks of treatment as measured by the NRS.

##### *4.3.2. Key secondary endpoints*

- Change in mean average pain intensity from baseline to Week 4 as measured by the NRS.
- Change in non-pain neuropathic signs after 12 weeks in patients as assessed by change in the UENS.

##### *4.3.3. Secondary endpoints*

- Change in weekly mean worst pain from baseline to Week 12 and Week 4 as measured by the NRS.
- Proportion of patients achieving  $\geq 30\%$  and  $\geq 50\%$  improvement in mean NRS score from baseline to Week 4 and to Week 12.
- Change in mean BPI-SF pain interference score from Pre-Treatment/Day 1 to Week 12.
- Change in mean BPI-SF pain interference score from Pre-Treatment/Day 1 to Week 4.
- Change from baseline to Week 12 in the NTSS-6.
- Change from baseline to Week 12 in Norfolk diabetic QOL-DN score.
- PGIC at Week 4 and Week 12.
- Rescue medication (acetaminophen) use.

#### 4.3.4. *Exploratory endpoints*

The exploratory endpoints for this study are:

- Change in intraepidermal nerve fiber density (IENFD) from baseline to Week 24 will be analyzed in a subgroup of approximately 120 patients at selected sites. Note that placebo subjects will have received ricolinostat for 12 weeks, while treated subjects will have received ricolinostat for 24 weeks. There are 4 comparisons of interest for this analysis:
  - Change from baseline in the IENFD in the group of approximately 60 patients that received ricolinostat for 24 weeks.
  - Change from baseline in the IENFD in the group of approximately 60 patients that received ricolinostat for 12 weeks.
  - The difference in the change from baseline in the IENFD in the Intent-to-Treat population at Week 24.
- Other exploratory endpoints may be identified at the time of analysis of the study data.

#### 4.4. **Safety assessments**

Safety will be assessed throughout the study by the monitoring for and recording of adverse events (AE), clinical laboratory test results (hematology, biochemistry, and urinalysis), vital sign measurements (systolic and diastolic blood pressures, pulse, respiratory rate, and temperature), ECG, physical examination, and height and weight findings as per the procedures detailed in the Schedule of Assessments (Exhibit 3).

##### 4.4.1. *Adverse events*

An adverse event (AE) is defined as any unfavorable and/or unintended medical occurrence that presents at any time from when the informed consent is signed through the final follow-up visit or earlier discontinuation (whichever comes first), regardless of relationship to the investigational product.

A *treatment-emergent adverse event* (TEAE) is any event that occurs after the start of study drug or was present at baseline and worsened after taking study drug.

*Serious adverse events* (SAE) are the subset of adverse events that are deemed by Regenacy or the Investigator to have resulted in any of the following: death, placing the patient at immediate risk of death, an inpatient hospitalization, a prolongation of existing hospitalization, a persistent or significant incapacity or disruption of the ability to conduct normal life functions, a congenital anomaly or birth defect, or an event that requires significant medical intervention to avoid those outcomes listed above.

*Suspected adverse reactions* are the subset of AEs for where this is a reasonable possibility that the investigational product caused the adverse event.

An *unexpected AE* is any suspected adverse reaction that is not listed in the current investigator's brochure (IB) or for which the severity is more extreme than what is listed in the IB; or is inconsistent with the general investigational plan or current application if the IB is not available.

*Events of special interest (ESI)*: The following events are defined to be of special interest: anemia, leukopenia, thrombocytopenia, renal impairment, congestive heart failure, and suicidality.

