## **9.6 Safety Extension (Week 12 to Week 24)**

From Week 12 to Week 24, all patients will receive ricolinostat 120 mg daily. Patients will return to the clinic as outlined in the schedule of events and at each visit procedures specified in the schedule of events for that visit will be performed.

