#### **10.3.7 Safety Analyses**

AEs will be coded using the Medical Dictionary for Regulatory Activities (MedDRA) by System Organ Class (SOC) and preferred term (PT). Only treatment-emergent AEs (TEAEs) will be

included in summary tables. A TEAE is defined as any AE that occurs after the start of study drug or was present at baseline and worsened after taking study drug.

The number and percent of patients with at least one 1) AE, 2) severe AE, 3) SAE, 4) AE leading to discontinuation, and 5) treatment-related AE will be presented by treatment arm for the Safety Population. The number and percent of patients with AEs will be presented by MedDRA SOC and PT for each treatment arm and overall. AEs will also be summarized by PT; by SOC, PT, and severity; and by SOC, PT, and relationship to study treatment. SAEs and AEs leading to discontinuation will also be presented.

The counts and percentages for AE summary tables will be based on the Safety Population. Patients with multiple unique events will be counted once per each unique PT and each unique SOC. If a patient has more than one AE that is coded to the same PT, the patient will be counted only once (using the maximum severity assigned) for that PT.

Observed values and change from baseline will be presented by visit and treatment group for hematology and chemistry laboratory tests. The number and percent of patients with hematology, chemistry, and urinalysis results outside the normal range will be presented by visit for each treatment arm. A second table will present shifts with respect to the lower limit of normal; the table will be repeated for shifts with respect to the ULN. Laboratory tests with categorical results that cannot be analyzed by change from baseline or shift table analysis will not be included in these summaries, but will be listed. Another table will present findings of special interest, including selected hematology and serum chemistry abnormalities relevant to the assessment of safety.

Descriptive statistics for vital signs and ECG results will be presented by treatment group.

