### 11.10.2.2 Adverse Events of Special Interest and Monitoring Procedure

The following AEs are designated as events of special interest, and, if observed as treatment-emergent during the study, should be addressed as described below: Anemia, leukopenia, neutropenia, thrombocytopenia, renal impairment, congestive heart failure, suicidality.

Observation	Risk Management
Clinical Laboratory Parameters for Adverse Events of Special Interest	
Cardiac Conduction: QTcF $\geq$ 500 ms or QTcF increase from baseline $\geq$ 60 ms and QTcF $\geq$ 480 ms	
 
For any observed case, the investigator should repeat the ECG assessment twice and compare the average of these 3 measurements of QTcF to the average of the 2 pre-treatment (i.e. screening and baseline) QTcF values
 
If confirmed, patient should be discontinued and appropriate follow-up instituted
 

Anemia: Hemoglobin decrease from baseline $> 2$ g/dL, or a decrease from baseline of at least 1.0 g/dL to a value below 11.5 g/dL (female) or 13 g/dL (male)	
 
For any observed case, repeat laboratory test within one week to confirm: 
 
If the abnormality persists on repeat laboratory test, refer to section 11.10.2.2.1 for additional laboratory monitoring and initiate appropriate medical work-up to assess potential causes.
 
 
 

Leukopenia: White blood cell count $< 2500/\text{mm}^3$ ; or a decrease from baseline $> 1500/\text{mm}^3$	
Neutropenia: Neutrophil count $< 1250/\text{mm}^3$ ; or decrease from baseline $> 500/\text{mm}^3$	
Platelet count $< 100,000/\text{mm}^3$ ; or a decrease from baseline $> 50,000/\text{mm}^3$	
eGFR $< 30 \text{ ml/min}/1.73 \text{ m}^2$	
 
Confirm with repeat test within one week; if confirmed, patient should be discontinued and appropriate follow-up instituted
 

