## 1. Introduction

This statistical analysis plan (SAP) describes the planned analyses for Regenacy's Protocol REGY-DN-201, entitled "A Phase II, Randomized, Double-Blind, Placebo-Controlled, Parallel Group Study of Ricolinostat in Patients with Painful Diabetic Peripheral Neuropathy". This SAP is based on version 5 of the protocol, dated September 24, 2021.

This SAP is to be interpreted in conjunction with the protocol. Should the SAP and protocol be inconsistent with respect to the planned analyses, the language of the SAP is governing. If the final clinical study report (CSR) contains changes to any planned statistical analyses, the justification for any such differences will be fully documented in the CSR.

The statistical principles applied in the design and planned analyses of this study are consistent with the International Conference on Harmonization (ICH) guidelines E9 (Statistical Principles for Clinical Trials) [1].

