### **11.2. Clinical laboratory evaluations**

Each laboratory value and change from baseline (when appropriate) will be summarized in tables and figures for hematology, blood chemistry and urinalysis for each treatment at Screening, discharge, and end of study. Boxplots of laboratory values will be provided. Shift tables may also be provided.

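### The SAP drops neutropenia from the events of special interest and names no double-blind on-treatment visit in its laboratory summaries

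*SAP*

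**What the plan says.** Protocol 11.10.2.2 names the events of special interest as "Anemia, leukopenia, neutropenia, thrombocytopenia, renal impairment, congestive heart failure, suicidality". SAP 4.4.1 says: "The following events are defined to be of special interest: anemia, leukopenia, thrombocytopenia, renal impairment, congestive heart failure, and suicidality". SAP 11.1 then plans a frequency table, by treatment group, of all events of special interest. On precedence, the SAP Introduction says: "Should the SAP and protocol be inconsistent with respect to the planned analyses, the language of the SAP is governing".

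For laboratory data, Protocol 10.3.7 says: "Observed values and change from baseline will be presented by visit and treatment group for hematology and chemistry laboratory tests". It also plans counts of out-of-range results by visit and arm, and it commits to shift tables: "A second table will present shifts with respect to the lower limit of normal", repeated for the upper limit. A further table is to show laboratory findings of special interest. SAP 11.2 instead summarises haematology, chemistry and urinalysis "for each treatment at Screening, discharge, and end of study" and adds: "Shift tables may also be provided".

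SAP Exhibit 3 schedules haematology at Screening, Day 1 and Weeks 1, 2, 4, 8, 12, 14, 18, 24 and 28. Chemistry and urinalysis are drawn less often.

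**The concern.** Safety is part of the primary objective, and the protocol pays specific attention to neutrophils. A low count is an exclusion criterion, Protocol 11.10.2.2.1 sets neutrophil thresholds for staying on drug, and Protocol 11.9 mentions episodes of neutropenia in earlier ricolinostat studies (attributed there to the malignancy and the concurrent chemotherapy). A special-interest table without neutropenia would be incomplete in a place where a reader would look for it, and the SAP gives no reason for leaving it out.

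The laboratory timepoints matter because the randomised comparison lasts only to Week 12. After that, Protocol 9.6 says: "From Week 12 to Week 24, all patients will receive ricolinostat 120 mg daily". A summary plan that names no on-treatment visit before the switch does not specify the haematology comparison that the design supports.

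**Working it through.** The documents state no figure for this point, so the check is a comparison of texts with simple counts.

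**1. The two lists.**

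| Event | Protocol 11.10.2.2 | SAP 4.4.1 |
|---|---|---|
| Anaemia | yes | yes |
| Leukopenia | yes | yes |
| Neutropenia | yes | **no** |
| Thrombocytopenia | yes | yes |
| Renal impairment | yes | yes |
| Congestive heart failure | yes | yes |
| Suicidality | yes | yes |

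The protocol has 7 terms and the SAP 6, in the same order. Of the blood-count events, 4 − 3 = 1 is missing.

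**2. Does the leukopenia row stand in for it?** The protocol defines neutropenia as a neutrophil count below 1250/mm³ or a decrease of more than 500/mm³. It defines leukopenia as a white cell count below 2500/mm³ or a decrease of more than 1500/mm³. If the other white cells stay constant, the white cell decrease equals the neutrophil decrease. A fall of more than 500 and up to 1500 then meets only the neutropenia criterion, unless the white cell count itself drops below 2500. An example with assumed counts: neutrophils go from 2600 to 1200 and other white cells stay at 2900.

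- Neutrophils: 2600 − 1200 = 1400, above 500, and 1200 is below 1250. Both neutropenia criteria are met.
- White cells: 2600 + 2900 = 5500 falls to 1200 + 2900 = 4100. The decrease of 1400 is not above 1500, and 4100 is not below 2500. Neither leukopenia criterion is met.

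So leukopenia is not a reliable substitute. How often this would happen cannot be derived from the documents.

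**3. The laboratory timepoints.** The SAP 11.2 wording set against Exhibit 3:

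- Screening is a scheduled visit, before treatment.
- Discharge does not appear anywhere in the schedule.
- End of study is Week 28 for completers (Protocol 9.7.2), after both arms have taken ricolinostat.

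| Test | Double-blind on-treatment visits in Exhibit 3 | Named in SAP 11.2 |
|---|---|---|
| Haematology | Weeks 1, 2, 4, 8, 12 (5) | 0 |
| Chemistry | Weeks 1, 4, 12 (3) | 0 |
| Urinalysis | Week 12 (1) | 0 |

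**4. Shift tables.** The protocol says they will be presented; the SAP says they may be. Where the two differ, the SAP's weaker wording governs.

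**5. Likely origin.** Other parts of SAP section 11 do not fit this trial either. It names 180 µg and 120 µg groups, although the trial has a single 120 mg arm. It also summarises vital signs and ECGs at hours after dosing that the schedule mostly does not collect. This suggests that SAP 11.2 was carried over without being adapted. That is an inference; the documents do not say so.

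**The case against.** The best defence is that little is lost in practice. Protocol 11.10.2.2.1 has confirmed events recorded on the adverse event form and flagged as being of special interest. Neutropenia therefore still appears in the treatment-emergent tables, and a programmer working from the flag might include it in the special-interest table anyway. The data monitoring committee works from the protocol's list (Protocol 10.3.8). The SAP Introduction also asks to be read together with the protocol, and nothing in the SAP contradicts the protocol's out-of-range counts or its special-interest laboratory table. All of this stands, and it limits the consequence. It does not correct the governing list.

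A reader might infer from SAP 11.2 that no placebo-controlled laboratory data would be shown at all. The documents do not support that. SAP 5.1 locks laboratory records through Week 12 at the first lock and excludes later data from that analysis, so the end of study there need not mean Week 28. SAP section 11 also says that safety analyses include all results from randomisation onward.

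A reader might also want neutropenia split into low counts and falls that stay above the limit, because the protocol accepts either as an event. That is a reporting preference, not an error in the plan. Protocol 11.10.2.2.1 says these events serve monitoring and should not be used to infer a relationship to drug. Mixing the two kinds does not bias the comparison between arms, and its size depends on count variability that the documents do not give. A split on the first two samples alone would also ignore the third and fourth samples, which the protocol counts.

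**Conclusion.** Wrong as written, minor. Read literally, the SAP leaves 1 of the protocol's 4 blood-count events out of the special-interest table. In SAP 11.2 it names a visit that does not exist and 0 of the 5 double-blind on-treatment haematology visits, and it turns committed shift tables into optional ones. These conclusions rest on the text and on the SAP's own precedence rule, with no assumed values; only the leukopenia example uses assumed counts. The documents do not support a claim that neutropenia data would be lost or that the randomised laboratory comparison could not be made. The defect lies in what the SAP specifies.

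**What to change.** 1. SAP 4.4.1: add neutropenia to the events of special interest, so that the SAP 11.1 table matches Protocol 11.10.2.2.
2. SAP 11.2: replace the three timepoints with the visits scheduled for each test in Exhibit 3, by treatment group. One common visit list would be wrong, because the tests follow different schedules:
   - haematology: Screening, Day 1, Weeks 1, 2, 4, 8, 12, 14, 18, 24, 28;
   - chemistry: Screening, Day 1, Weeks 1, 4, 12, 24, 28;
   - urinalysis: Screening, Day 1, Weeks 12, 24.
3. SAP 11.2: present the double-blind visits through Week 12 as the randomised comparison.
4. SAP 11.2: make the out-of-range counts and shift tables of Protocol 10.3.7 mandatory.

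The cost is SAP wording and table layouts, using samples that are already scheduled. The change is best made before unblinding, so that the tables are not shaped by the results.

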#### 4.4.2. *Laboratory safety assessments*

The laboratory tests that will be collected at the timepoints specified are presented in the schedule of events (Exhibit 3). Abnormal Screening laboratory values that appear to be spurious, or that are the result of a transient event, may be repeated once; in this circumstance the repeated value will be utilized as the value of record for analysis purposes.

#### 4.4.3. *Vital signs*

Vital signs will be measured as per the schedule of events (Exhibit 3). At indicated timepoints, temperature, respiration rate, pulse, and blood pressure will be measured while patient is sitting after a minimum 5-minute rest. Standing pulse and blood pressure will be obtained following sitting vital signs.

Descriptive statistics for vital signs will be presented by treatment group.

#### 4.4.4. *Electrocardiogram (ECG)*

A 12-lead ECG will be performed at Screening Evaluation, Pre-Treatment baseline, Week 1, Week 12, and Week 24 after the patient has been resting in the supine position. On Day 1 (Pre-Treatment Baseline), an additional 12-lead ECG will be obtained 1 hour (+/- 10 minutes) post-dose.

Descriptive statistics for ECG results will be presented by treatment group.

#### 4.4.5. *Physical examinations*

A standard physical examination will occur in accordance with the schedule of events (Exhibit 3). Post-baseline physical examinations will assess changes from the prior visit or new concerns.

Assessment of skin integrity and wound healing, if applicable, will also be performed at the times indicated in Exhibit 3. Skin breaches and wounds will be examined, and the following parameters recorded: location, size, depth, and evidence of erythema, edema, warmth, odor, or drainage.

#### 4.4.6. *Height and weight*

Height and weight will be measured at the times indicated in the schedule of events (Exhibit 3) and will be used to calculate BMI.

## 5. **Database lock and unblinding**

### 5.1. **Blinded data review (BDR) review of selected data prior to database lock**

The clinical database will undergo a “soft lock” when the last patient that is still in the randomized control period has completed their Week 12 visit or early study discontinuation. During the soft lock, all variables will be locked for changes except for those variables that will continue collection during the 12-week open label period (e.g., adverse events, laboratory assessments, IENFD, etc.); the data from these variables will be locked for all records collected

prior to and through the Week 12 visit. To avoid inadvertent unblinding, any data collected after Week 12 during the open label period will remain unlocked, excluded from analysis, and blinded with respect to treatment group assignment.

After the soft lock and prior to accessing the randomized treatment assignments, a review of locked blinded data will occur to accomplish the following objectives: 1) assess the impact of missing data on study analysis, 2) assess and correct the database for inconsistent data, 3) identify the per-protocol population and, 3) finalize the methods needed for analysis of the study objectives while still blinded to results. Outputs consisting of tables, listing, and figures without treatment groups or with randomly generated treatment group assignments will be produced, as needed, to accomplish the blinded data review.

A second (unblinded) data review may occur after the final patient has completed the Week 28 visit or early study discontinuation. The data collected after the initial soft lock will be analyzed during the second data review. The procedures and objectives for this data review are the same as those described above after study completion of the randomized control period.

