## **5.2. Database lock**

After completion of all BDR procedures, validation of the project databases and Regency's approval of the BDR, the clinical database will be locked. After the database lock and the authorization for unblinding, the treatment codes will be merged to the analysis datasets. After database lock, final endpoint analysis may commence. Note that there will be two separate database locks that follow soft locks and data reviews; one after the randomized control period has completed and one after the Week 28 follow-up period has completed.

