## **5.3. Authorization for unblinding**

The fire-walled unblinded analysis team at Medpace will have access to the treatment codes for analysis purposes. After database lock, top-line results will be available to Regency.

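### SAP 5.1 labels the second data review unblinded but gives it the blinded review's task of finalising methods; the two must be reconciled for post-Week 12 data

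*SAP*

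**What the plan says.** SAP 5.1 describes a first review after the Week 12 soft lock and before anyone accesses the treatment assignments. Its tasks are to weigh the effect of missing data, correct inconsistent records, identify the per-protocol population, and "finalize the methods needed for analysis of the study objectives while still blinded to results". Its outputs show no treatment groups, or dummy ones. Data collected after Week 12 stay unlocked, masked and out of the analysis.

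The section then adds: "A second (unblinded) data review may occur after the final patient has completed the Week 28 visit or early study discontinuation". On the purpose of that review: "The procedures and objectives for this data review are the same as those described above after study completion of the randomized control period". On its content: "The data collected after the initial soft lock will be analyzed during the second data review".

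SAP 5.2 provides for two locks, "one after the randomized control period has completed and one after the Week 28 follow-up period has completed", and states: "After the database lock and the authorization for unblinding, the treatment codes will be merged to the analysis datasets". SAP 5.3 places the codes with a fire-walled team at the CRO and adds: "After database lock, top-line results will be available to Regency".

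Protocol 10.3.2 describes a blinded review for the Week 12 lock only. Protocol 7.4.3 keeps sponsor and CRO staff blinded until database lock without saying which of the two locks is meant. SAP 1 makes the SAP govern where the documents differ on planned analyses.

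**The concern.** Finalising methods and correcting data before unblinding prevents those decisions from being shaped by the results. SAP 5.1 states that principle for the first review and then hands the same tasks to a review it calls unblinded. Followed as written, decisions on data collected after Week 12 could be taken by people who know the original arm and have seen the pain results.

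The main efficacy measure in that period is IENFD, biopsied at Day 1 and Week 24. Protocol 10.2.1.3 and SAP 4.2.8 both say it should help show whether the drug has a structural effect on peripheral nerves. Choices made with codes known would weaken that evidence.

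**Working it through.** The point is procedural, so the check is mainly a comparison of passages.

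**1. The conflict.** The first review's task is tied to being blind ("finalize the methods needed for analysis of the study objectives while still blinded to results"). The second review takes over the same procedures and objectives but is labelled unblinded. Both cannot hold.

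**2. The order of events (SAP 5.1 to 5.3).** Week 12 soft lock; first review, blind; first lock; codes merged and top-line results released; Week 24 and Week 28 data completed; second soft lock and second review; second lock. Codes from the first lock therefore exist before the second review. SAP 5.1 also has the later data analysed during that review, whereas SAP 5.2 has final endpoint analysis begin after lock.

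**3. What is already fixed.** Protocol 10.3.6 and SAP 10 both give the between-arm Week 24 IENFD test as an ANCOVA on change from baseline, with baseline density and treatment group, in the intent-to-treat population.

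**4. What is still open or inconsistent.**
- Biopsy site: Protocol 7.1 takes a thigh and an ankle sample at each timepoint. Neither Protocol 10.3.6 nor SAP 10 says which is analysed, or whether they are combined.
- Missing biopsies: SAP 6.1.5 has rules for the primary, UENS and secondary endpoints, but none for IENFD.
- Early-termination biopsies: Protocol 9.8 collects them between Weeks 12 and 24, while the Week 24 window in SAP Exhibit 4 is days 164 to 172.
- Baseline restriction: Protocol 6.3 and the synopsis endpoint require reduced IENFD at baseline; SAP 2.4 and 4.3.4 do not.
- Within-arm tests: Protocol 10.3.6 tests the ANCOVA intercept; SAP 10 uses a t-test. SAP 10 also mentions Week 12 IENFD, although no Week 12 biopsy is scheduled.

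**5. The sub-study's own figure.** Protocol 7.1 states about 80% power for an increase of 0.44 fibres/mm, SD 1.2, with at least 60 patients per arm. With a one-sample test at two-sided 0.05 (SAP 6.1.3) and n = 60:
- Normal approximation: Φ(0.44 × √60 / 1.2 − 1.96) = Φ(2.84 − 1.96) = 0.811.
- Noncentral t: 0.798.

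The figure reproduces, but for the within-arm test. Assuming the same 0.44 and 1.2 apply to the difference between arms, with 60 per arm:
- Φ(0.44 / (1.2 × √(2/60)) − 1.96) = Φ(2.01 − 1.96) = 0.52 (t-test 0.51).

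The sub-study's power thus rests on the within-arm test, which is one of the items the documents leave inconsistent.

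**6. An illustration of the risk.** Assume no true effect, and that one of the two biopsy sites is picked after seeing both results by arm. The chance that at least one is nominally significant is 1 − P(|Z₁| < 1.96 and |Z₂| < 1.96):
- independent sites: 1 − 0.95² = 0.0975
- correlation 0.5: 0.091
- correlation 0.9: 0.070

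The documents give no correlation and do not say such a choice would be made. These numbers show the kind of risk; they do not estimate bias in this trial.

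**The case against.** The strongest reply is that the unblinded label is a drafting slip. The section is titled as a blinded review, the second review uses the same procedures (which include masked outputs), and the word may refer to the open-label period. The review is also optional. This is plausible, but the SAP governs and its text still needs correcting. SAP 5.2 describes both locks as following data reviews, so the optional wording gives limited comfort.

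A second reply is that IENFD is one of the study objectives (SAP 2.4), so its methods already fall to the first, blinded review. That is a fair reading and makes the repair easy. It does not remove the second review's stated mandate to finalise methods again.

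A third is that safeguards exist: masking of post-Week 12 data, the fire-walled team, and the protocol's blinding rule. They count, but none says how long it lasts across two locks, and SAP 5.1 does not say who conducts the second review.

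A reader might infer that the whole randomised Week 24 IENFD comparison can be settled with codes known. The documents do not support that, because its model, covariates and population are named in both. Nor do they say that those correcting data would know each patient's arm: SAP 5.3 promises the sponsor top-line results and does not mention patient-level codes. The comparison also sets 24 weeks of ricolinostat against 12, with no untreated arm at Week 24, and Protocol 7.1 puts most weight on the within-arm change. These limits stand and narrow the point.

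**Conclusion.** The conflict in SAP 5.1 is real and must be reconciled, but it is a minor point. The exposure is confined to corrections of data collected after Week 12 and to the open or inconsistent IENFD choices listed in step 4 above. The IENFD analyses affected involve about 120 patients and are exploratory, with nominal p-values (Protocol 10.3.6, SAP 8.2).

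The Week 4 and Week 12 efficacy results are unaffected: their data and methods are settled at the first, blinded review. It would be wrong to infer a threat to the primary result or to the control of type I error. No size of bias can be computed. The conclusion assumes only that SAP 5.1 would be followed as worded; if the label is a slip, what remains is a correction of the text.

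**What to change.** Amend SAP 5.1 to state that all IENFD and other post-Week 12 methods, populations and data-handling rules are finalised at the first blinded review. For IENFD this means naming the biopsy site analysed, the handling of missing and early-termination biopsies, whether reduced baseline density is required, and the within-arm test and its timepoint. Remove method-finalising from the second review and limit it to data queries, made by staff without access to the original assignment until the second lock.

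The cost is one SAP paragraph, with no change to sample size or to the timing of the Week 12 analysis. The one burden is that the fire-wall must be kept in place from the Week 12 lock to the second lock.
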